Patients will be identified in the Hematology Clinic of the Special Program at Mount Sinai Hospital, where consent will be obtained. Patients will be randomized immediately following consent. Randomization has been developed for RedCap to allocate the patient into one of the two strategies in a 1:1 ratio, with the assistance of a statistician from Princess Margaret Hospital. Following delivery, the research assistant will dispense the assigned medication to the participant. Blinding or masking of treatment allocation will not be used in the pilot but a placebo control for ASA is intended for the definitive trial.

Baseline Assessment

Baseline assessments will be undertaken at the time of randomization and include age, weight, parity, indication for VTE prophylaxis, gestational age at delivery, medications and delivery complications. Baseline laboratory tests at the time of delivery will include complete blood count, serum creatinine level, coagulation profile and alanine aminotransferase. This limited testing is intended to reflect a pragmatic approach to this trial.

Primary Outcomes:

1. Potential enrollment rate (patients eligible)
2. Consent rates (patients approached/consent obtained/rationale for non-consent)
3. Adherence to study protocol (incidence and reasons for nonadherence, withdrawal of consent, rates of contamination and utilization of co-interventions).
4. Missing data

Secondary Outcomes:

1. VTE event rate three months following delivery
2. Bleeding event rate three months following delivery
3. Quality of life (QoL) assessment using the modified Duke Anticoagulation Satisfaction Scale (Appendix) at delivery and three and six weeks postpartum

Confirmation of VTE

VTE must be confirmed either by Doppler ultrasound or V/Q scan or computer tomography (CT). Imaging will not be performed on all patients, only those with symptoms. For the definitive trial, imaging will be adjudicated.

Bleeding outcomes

Bleeding will be reported according to the International Society on Thrombosis and Hemostasis (ISTH) scoring system (<https://bleedingscore.certe.nl/>) (Schulman *et al.*, 2005; Schulman *et al.*, 2009). Bleeding will be assessed at 3 and 6 weeks postpartum using a telephone questionnaire.

Follow up duration

All patients will be followed until 3 months postpartum. Patients will be contacted by telephone at 3 weeks, 6 weeks and 12 weeks after delivery.

Participant trial discontinuation

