Data Management: Appropriate training and security measures will be completed. The case report form will be developed electronically and piloted. All patient-related information, including case report forms, will be kept strictly confidential. All records will be kept in a secure, locked location, and only research staff will have access to the records. Patients will be identified only by means of a coded number specific to each patient. All computerized databases will identify patients by numeric codes only, and will be password protected and housed in a locked office.

Data Safety Monitoring Committee: A data safety monitoring board will be assembled, consisting of one hematologist and one obstetrician. Any VTE or bleeding event will be reviewed by this committee.

Ethics: The study will be submitted for research ethics board approval. Virtual consent during the current COVID-19 pandemic is currently feasible and is an option for this trial.

Safety: I will be responsible for ensuring that the patient or her substitute decision-maker understands the risks and benefits of participating in the study, answering any questions the patient or family member may have throughout the study and sharing any new information in a timely manner that may be relevant to the patient's willingness to continue her participation in the trial. All study participants will be informed of the objectives of the study and the potential risks. Consent forms will also discuss the benefits and risks of this pilot trial and the definitive study. All patients will be informed of the signs and symptoms of VTE that would necessitate emergency room visits as participants in both arms may develop a VTE.

Significance: This single center pilot feasibility study will address enrollment, adherence of two anticoagulant strategies postpartum in women who require prophylaxis with LMWH. The results of this study will be used to design a large definitive multicentered trial. All clinical outcomes from the pilot study will be used to inform the final trial design. Demonstrating the non-inferiority of ASA and LMWH to LMWH will lead to a shorter course of LMWH postpartum, potentially reducing bleeding risk, need for subcutaneous injections as well as cost while improving quality of life. If the definitive trial does not show inferiority, the results will provide evidence that six weeks of postnatal thromboprophylaxis is warranted.

Trial Schematic Timeline

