Participant	Screening Week -8 to Day -1	Dosing Day 1	3-week phone call ± 5 days	6-week phone call (end of study) ± 5 days	3-month phone call ± 5 days	Early discontinuation visit
Informed Consent	X	---	---	---	---	---
Inclusion / Exclusion criteria and Eligibility	X	---	---	---	---	---
Baseline demographics	X	---	---	---	---	---
Concurrent medications	X	---	X	X	X	X
Weight/BMI	X	X	X	X	X	X
Delivery Data: Type of Delivery/ Complications	---	X	---	---	---	---
Laboratory Data: Complete blood count / Creatinine / INR / aPTT / ALT	---	X	---	---	---	---
Drug dispensation	---	X	---	---	---	---
Adherence assessment	---	---	X	X	---	X
Bleeding Assessment Score	---	---	X	X	---	X
Quality of life assessment	---	---	X	X	---	X

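### The schedule has no active VTE item at any contact and no bleeding assessment at the 3-month call, although both event rates are 3-month outcomes

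*Protocol*

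**What the plan says.** Secondary Outcomes in the Protocol lists "VTE event rate three months following delivery" first and "Bleeding event rate three months following delivery" second. Follow up duration states "All patients will be followed until 3 months postpartum" and "Patients will be contacted by telephone at 3 weeks, 6 weeks and 12 weeks after delivery".

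On how events come to light, the text treats the two outcomes differently:

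- **Bleeding.** Bleeding outcomes says "Bleeding will be assessed at 3 and 6 weeks postpartum using a telephone questionnaire". It names no 3-month assessment.
- **VTE.** Confirmation of VTE names the accepted imaging tests and adds "Imaging will not be performed on all patients, only those with symptoms". The Safety paragraph says women will be told which symptoms call for an emergency visit. Data Safety Monitoring Committee says "Any VTE or bleeding event will be reviewed by this committee". None of these says how the trial finds out that an event has occurred.

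The Trial Schematic Timeline has 11 rows: consent, eligibility, demographics, concurrent medications, Weight/BMI, delivery data, laboratory data, drug dispensation, adherence, bleeding score and quality of life. One column is headed "6-week phone call (end of study", and a 3-month call follows it in the same table.

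**The concern.** An event rate is only as good as the procedure that looks for events. There is no routine imaging, so a VTE enters the data only if a symptomatic woman is diagnosed and the diagnosis reaches the trial. The protocol covers the first step and leaves out the second. A woman may be diagnosed at another hospital, or after the 6-week call, and no scheduled question is designed to pick that up. For bleeding the question exists at 3 and 6 weeks but not for the rest of the 3-month window.

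This could be passed off as detail left to the case report form, but the version history shows the table being used as the list of what is collected. Version 2.4 added medications at 3 months, version 2.5 added the bleeding score at 3 weeks, 6 weeks and early discontinuation, and version 2.6 removed quality of life from the dosing day. Staff who follow the table exactly would have no instruction to ask about VTE.

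The stake lies mostly beyond the pilot. Statistical analysis says the pilot patients' outcomes will be included in the definitive trial, and that a successful pilot leads to a full trial under the current protocol. That trial tests non-inferiority on VTE, where missed events blur the comparison.

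**Working it through.** **1. Marks in the schedule at the four contacts after dosing**

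| Item | 3-week call | 6-week call | 3-month call | Early discontinuation |
|---|---|---|---|---|
| Concurrent medications | X | X | X | X |
| Weight/BMI | X | X | X | X |
| Adherence | X | X | – | X |
| Bleeding score | X | X | – | X |
| Quality of life | X | X | – | X |
| VTE symptoms, imaging or diagnosis | no row | no row | no row | no row |

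VTE has an item at 0 of 4 contacts and bleeding at 3 of 4. The missing bleeding contact is the one that closes its stated outcome window.

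**2. Share of follow-up without a clinical-event item**

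With calls at 3, 6 and 12 weeks, the period after the 6-week call is (12 − 6)/12 = 50% of follow-up. Its only scheduled call carries neither a VTE nor a bleeding item.

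**3. Expected VTE events in the pilot**

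Inputs: N = 50 (Sample size calculation). Background gives a risk on postpartum prophylaxis of 1.7% (95% CI 1.2% to 2.7%) in women with prior VTE, and 0.2% (95% CI 0% to 1.2%) in high-risk thrombophilia. The inclusion criteria admit both groups, and the mix is not stated.

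Expected events = N × p:

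- All thrombophilia: 50 × 0.002 = 0.10
- All prior VTE: 50 × 0.017 = 0.85 (0.60 to 1.35 over the confidence interval)

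Chance of at least one event = 1 − (1 − p)^50:

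- p = 0.002: 1 − 0.998^50 = 0.10
- p = 0.017: 1 − 0.983^50 = 0.58 (0.45 to 0.75 over 1.2% to 2.7%)

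One missed event could take the observed result from 1/50 (2%) to 0/50. The exact 95% upper limits are 10.6% and 7.1%, so neither result says much about VTE risk in its own right.

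**4. Effect of under-capture on a risk difference**

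If a share s of events is captured, equal in both arms, then observed difference = s × true difference. The protocol gives no value for s, so the values below are assumptions. So is the true excess of 1.5 percentage points, chosen only to lie above the 1.0% margin, which is read here as percentage points.

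| s | Observed difference |
|---|---|
| 1.0 | 1.50 |
| 0.8 | 1.20 |
| 0.6 | 0.90 |

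The observed value falls below 1.0 once s is under 1.0/1.5 = 0.67. This describes a whole trial run with the same capture. The 50 pilot women would be only part of the definitive sample, whose size is not given, so their own contribution to such shrinkage would be smaller.

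If s differs between arms, the observed difference can move either way.

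The protocol states no figure on ascertainment, so there was none to reproduce.

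**The case against.** The strongest reply is that this is a feasibility pilot. Its four primary outcomes are enrolment, consent, adherence and missing data. Clinical endpoints are to be described only, and none of the four progression criteria (recruitment, adherence, compliance with procedures, loss to follow-up) uses VTE. All of that stands. A missed VTE cannot alter the decision to proceed, and a reader who took VTE to be the trial's main safety outcome would be going beyond the protocol, which lists it as a secondary outcome.

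A second reply is that silence does not prove the question goes unasked. Every woman is telephoned three times, concurrent medications are recorded at all four contacts after dosing and would tend to reveal new therapeutic anticoagulation, and the case report form is not shown. This also stands in part. A reader might infer that VTE data rest wholly on spontaneous reports, or that an event elsewhere would never reach the safety board. The protocol does not establish either. It does show that no active question is specified, and the medication item is an indirect prompt that records neither the diagnosis nor its date.

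A third tempting inference is that missed events would make the aspirin strategy look safer than it is. That needs either a true excess on aspirin or selective under-reporting in that arm, and the protocol shows neither. Both arms receive LMWH for the first three weeks. The Background places 61.1 + 16.3 + 9.9 = 87.3% of six-week VTE there, in the general postpartum population. In an open-label trial, women or staff could equally report more on the newer strategy.

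Finally, the 6-week label may have been meant as the end of study treatment, since the table itself schedules a later call. That is plausible, but the wording still conflicts with the stated follow-up.

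**Conclusion.** The gap is real and should be fixed, but it is no obstacle to the pilot's feasibility aims. The schedule provides no active VTE item at any contact after dosing and no bleeding assessment at the 3-month call, while the protocol promises both event rates at that time. The 6-week label adds an internal conflict over when follow-up ends.

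The supportable consequence is possible under-ascertainment of both 3-month rates, of unknown extent. Equal under-capture shrinks any true difference towards zero; unequal reporting could bias it in either direction. About 0.1 to 0.85 VTE events are expected in 50 women. The importance therefore comes less from the pilot's own VTE rate than from carrying these outcomes, and possibly this schedule, into a non-inferiority trial with a 1.0% margin.

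This rests on three assumptions: that staff follow the table as written; that the case report form adds no VTE question, which cannot be checked here; and that the Background risks, which come from women on prophylaxis, roughly describe the enrolled population over three months.

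**What to change.** - Add one row to the Trial Schematic Timeline for VTE (symptoms, imaging, diagnosis and date), marked at the 3-week, 6-week and 3-month calls and at early discontinuation. Ask it as a fixed question, worded identically in both arms, with a recorded answer even when negative, so that no event can be told apart from not asked.
- Mark the bleeding assessment at the 3-month call, and bring the Bleeding outcomes paragraph into line.
- State that every positive answer goes to the safety board.
- Reconcile the end-of-study label on the 6-week column with the 3-month follow-up.

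The cost is one schedule row, one extra mark, one relabel and the matching case report form items, all on contacts already planned. No new visit is needed. For women already past a call, the question can be put at their next one, though events not asked about at the time may be harder to date.

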APPENDIX: MODIFIED DUKE ANTICOAGULATION SCALE

During the past 3 weeks...	Strongly disagree	Disagree	Neither agree nor disagree	Agree	Strongly agree
Fear of bleeding while taking blood thinners limited my participation in vigorous activities.					
Fear of bleeding while taking blood thinners limited my participation in activities of daily living					
I was concerned about the possibility of excessive bruising while taking blood thinners					
Taking blood thinners limited my diet (e.g. food or drink, including alcohol).					
Taking blood thinners added stress to my life					
Taking my blood thinner was difficult to carry out					
Taking my blood thinner required a great deal of time to carry out					
Taking my blood thinner caused me a great deal of worry					
Taking my blood thinner caused me a great deal of irritation					
Taking my blood thinner caused me a great deal of frustration.					

Taking my blood thinner was a burden to me					
Taking my blood thinner negatively impacted my quality of life					
I have confidence that my blood thinner will protect my health (prevent blood clots, stroke, heart attack)					
I am satisfied with my blood thinner					

References

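### An early 6-week call can leave up to 5 of 42 treatment days without an adherence check, and the last contact (12 weeks or 3 months) does not reliably cover the three-month VTE and bleeding outcomes

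*Protocol*

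**What the plan says.** **Calls and windows.** The Trial Schematic Timeline lists a "3-week phone call ± 5 days", a "6-week phone call (end of study) ± 5 days" and a "3-month phone call ± 5 days". The adherence assessment and the Bleeding Assessment Score are marked at 3 weeks, 6 weeks and early discontinuation, but not at 3 months. The table has no row for VTE.

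**Last contact.** The section on follow-up duration states "All patients will be followed until 3 months postpartum" and then "Patients will be contacted by telephone at 3 weeks, 6 weeks and 12 weeks after delivery". The second statement carries no window.

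**Outcomes.** Adherence is among the primary outcomes, and adherence to study drug above 80% is one of the criteria for going on to the full trial (Statistical analysis). The two clinical event outcomes are "VTE event rate three months following delivery" and "Bleeding event rate three months following delivery". The section on bleeding outcomes places bleeding assessment at 3 and 6 weeks only.

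**Treatment.** Under Intervention, the control arm has one six-week course. The other arm has three weeks of LMWH and then three weeks of ASA.

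**Quality of life.** The scale in the Appendix has the recall stem "During the past 3 weeks".

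**The concern.** The 6-week call is the last scheduled look at adherence, yet it may be made before treatment is due to end. What happens on the remaining days is then not asked about at any planned contact. Those days fall in weeks 4 to 6, the only period in which the two strategies differ, so they bear directly on whether the switch to ASA is feasible.

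The later part of follow-up has a different problem. Two sections give two dates for the last contact, and one of them comes before the point at which the event rates are defined. The table calls the 6-week call the end of the study although follow-up runs on. Neither event outcome has a scheduled item at the last call.

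The pilot reports clinical events descriptively only. However, the Statistical analysis section says that success leads to a full trial under the current protocol and that these patients' outcomes will be included in it. There, VTE and bleeding are to be compared by a log-rank test, so an unclear end of follow-up would be carried forward.

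**Working it through.** The documents give no figure of their own to reproduce. The check is calendar arithmetic on the stated windows. Two assumptions apply: day 1 is about the day of delivery (the first injection is due within 12 hours), and 3 months is day 91 (range 90 to 92).

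**1. Windows as scheduled**
- 3-week call: 21 ± 5 = days 16 to 26.
- 6-week call: 42 ± 5 = days 37 to 47.
- 3-month call: 91 ± 5 = days 86 to 96.

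**2. Adherence days with no later scheduled check**
- Call on day 37: days 38 to 42 remain, 42 − 37 = 5 days.
- Share of the course: 5/42 = 11.9%.
- Share of the second phase (days 22 to 42): 5/21 = 23.8%.
- A woman who takes every dose to day 37 and then stops: 37/42 = 88.1% of the course, 16/21 = 76.2% of the second phase.
- If the 80% line were applied to each woman over the whole course, the gap could move her across it only if she had already missed 4 to 7 doses by day 37. With 4 missed, 33/37 = 89.2% is seen but 33/42 = 78.6% is true. With 3 missed, 34/42 = 81.0% stays above. With 8 missed, 29/37 = 78.4% is already below.

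**3. An early 3-week call**
- Call on day 16: days 17 to 21 follow it, but the 6-week call asks about adherence and bleeding again, so nothing need be lost.

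**4. Last contact**
- 12 weeks = day 84. Shortfall: 91 − 84 = 7 days (6 to 8 for day 90 to 92), or 7/91 = 7.7% of the period.
- The schedule's 3-month call at its earliest: 91 − 86 = 5 days short.

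**5. Bleeding**
- From an on-time 6-week call to day 91: 91 − 42 = 49 days with no scheduled score, 49/91 = 54% of the outcome period (44 to 54 days across the window).

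**6. VTE at stake**
- Inputs from Background: risk on prophylaxis 1.7% (1.2% to 2.7%); week 6 holds 2.4% of six-week VTE.
- Expected events: 50 × 0.017 = 0.85 (0.60 to 1.35).
- Days 38 to 42: 0.85 × 0.024 × 5/7 = 0.015 (0.010 to 0.023). The last contact could still pick these up.
- Days 84 to 91, if the week-6 rate persists: 0.85 × 0.024 = 0.020 (0.014 to 0.032).

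**7. Recall period of the quality-of-life scale**
- A 3-week call on day 26 looks back over days 6 to 26, which includes 5 second-phase days.
- A 6-week call on day 37 looks back over days 17 to 37, which includes 5 first-phase days.

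**The case against.** A symmetric window of ± 5 days is ordinary, and only an early call loses anything. A woman who formally discontinues has a discontinuation contact that records adherence, bleeding and quality of life, so only a silent stop is missed. Any VTE or bleeding event also goes to the safety committee, whatever the call dates. These points stand, although committee review acts on events that reach it and schedules no questioning of participants.

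Four stronger readings are tempting, and the documents do not support them.

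- **Every call loses data.** It does not. The 6-week call can recover what an early 3-week call misses, and the last contact can still pick up VTE that follows an early 6-week call.
- **A woman who stops on day 37 fails the 80% criterion.** The 76% uses a 21-day denominator that the protocol never states. Over the whole course she is at 88%. The protocol also gives no rule that counts unobserved days as adherent.
- **The last call may be on day 79, 12 days (13%) short.** That applies the schedule's window to a 12-week date that carries none. The supported shortfalls are about 7 days for the 12-week date and at most 5 days for the 3-month call.
- **The windows are what cut bleeding short.** The larger cause is that no score is scheduled after 6 weeks. Moving the calls would not repair that.

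**Conclusion.** The point holds in a limited form, and the schedule should be corrected.

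- **Adherence:** up to 5 of 42 days (12% of the course, 24% of the second phase) can have no scheduled check, for a primary outcome and go criterion. This needs an early 6-week call and a woman who stops without discontinuing formally. How often that would happen cannot be told from the document. What is missed can only be late non-adherence.
- **Last contact:** 12 weeks and 3 months are different dates. The first ends about 7 days before the point at which both event rates are defined.
- **Bleeding:** about 49 days of a three-month outcome have no scheduled score, even with exact timing. This is the largest gap.
- **VTE:** a three-month outcome with no item in the schedule. The number lost to timing is negligible, about 0.02 expected events in 50 women. That figure assumes that the general postpartum weekly pattern applies to these women and that the week-6 rate persists to three months. The reason to act is consistency and carry-over into the definitive trial, not bias in the pilot's VTE rate.

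**What to change.** 1. **6-week call:** make it no earlier than day 42, for example 0 to +7 days. Alternatively, keep the window and ask at the last call about adherence through day 42.
2. **Last contact:** use one date, 3 months and not before about day 91, in both the follow-up section and the Trial Schematic Timeline.
3. **Label:** remove the end-of-study wording from the 6-week call.
4. **Event outcomes:** add bleeding and VTE ascertainment to the last call, and bring the section on bleeding outcomes into line.
5. **3-week call:** leave the window as it is, but record adherence and quality of life there for the first phase only. A one-sided window at 3 weeks would pull more second-phase days into the recall period.

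**Cost.** These are wording and schedule edits, plus a few more questions at the last call. The calling window narrows: 0 to +7 gives 8 possible days (42 to 49) in place of 11 (37 to 47), and the last call shifts in the same way. That may produce more out-of-window calls, which matters because compliance with procedures above 80% is itself a go criterion. A 6-week call on day 49 would bring up to 7 off-treatment days into a three-week recall, so the quality-of-life question there should refer to the second treatment phase. Asking about adherence only at the last call avoids the narrower 6-week window but relies on recall over about 7 weeks (91 − 42 = 49 days).
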